### Model Results Presentation

Once the posterior distributions have been estimated using SAS, the following key interim analysis inferences and predictions will be estimated using the associated posteriors:

- Univariate features of the posterior probability distribution (mean, StdDev, MCMC error, ratio of MCMC error/StdDev, median, and 5th and 95th percentiles used for 90% equal-tailed credible intervals (CrI)) will be calculated for each model parameter. The estimated dose response curve with a 90% CrI will be graphically displayed, and overlaid on the

**Bayesian Statistical Analyses**

observed data.

- The range of possible doses: 250, 500, 1000, 2000, 4000 and 6000 mg for Part 1 and 1000, 2000, 4000 mg for Part 2.
  - At each chain of the MCMC algorithm in the SAS program (as described above), we will obtain an estimate for the mean AUC[0-t] or Cmax at each dosing level (as in the previous bullet for Part 1) with a 90% CrI using the 5th and 95th percentiles. This will be calculated as found in the model formulation (1) using the sampled parameter values.
  - These point estimates will be displayed on a figure with the dots connected. If the associated posterior distributions for the predicted responses at the dose levels are skewed then the point estimates used to generate the dose response curve plot will be generated using the median as a measure of central tendency. The 5th and 95th percentiles will still be used for the 90% CrI about the parameter.
  - The observed data will be overlaid on this curve at the doses which were explored.
- The Bayesian inferential probability that mean AUC[0-t] and Cmax values will be greater than 2875 h.µg/mL and 2270 µg/mL (maximum exposures at the NOAEL dose in the rat for AUC and the monkey for Cmax), respectively, will be calculated for each dose level in Part 1.
  - The Bayesian predictive probability that an individual subject will have AUC[0-t] and Cmax values greater than 3460 h.µg/mL and 2590 µg/mL (maximum exposures at the NOAEL dose in the rat for AUC and the monkey for Cmax), respectively, will be calculated for each dose level in Part 1.

All the outputs discussed above and listed below are used together with safety and tolerability data to aid the next dose selection.

The mean, median, and 5th and 95th percentiles (90% CrI) for each model parameter and prediction will be tabulated.

Figures will be produced for posterior dose-response model for AUC[0-t], and Cmax (with 90% CrI), respectively as discussed above in inference bullet.

A Listing for PK parameters AUC[0-t] and Cmax in Part I single dose phase will be provided.

In addition, the above listed inferences and predictions will be performed for PK parameters AUC[0-24] and Cmax in Part 2 repeat dose phase. The corresponding tables, figure and listing listed above will also be produced.

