### Bayesian Statistical Analyses

- $\epsilon_{ij}$  is a random error term, with mean zero and variance  $\sigma^2$ .

In general, Bayesian inference seeks to quantify the probability distributions of model parameters such as the  $(\theta_1, \theta_2, \sigma)$  defined in Equation (1). The present inference will incorporate a normal-Half-Normal prior distribution, to express the prior information about the parameters  $(\theta_1, \theta_2, \sigma)$ . Due to limited information available about the GSK3342830 compound, an informative prior with large variance will be used. For ease of parameterization for the normal distribution in computer programming, use  $\nu = \sigma^{-2}$  as the precision. Model parameters are assumed *a priori* to be independent.

**Table 9** Prior Distributions

Model Parameter	Prior
$\theta_1$ (intercept)	~ Normal(-1, precision= $10^{-6}$ )*
$\theta_2$ (slope of log-dose)	~ Half-Normal(0, precision= $10^{-5}$ , lower=0)*
$\nu$ (precision)	~ Gamma(1, iscale=5)*

All model parameters are *a priori* independent.

\*SAS Version 9.4 will be used for the Bayesian analysis, specifying the normal distribution using mean and precision. Because of the assumption that population mean PK parameter values increase as a higher dose is administered, let  $\theta_2$  have a Half Normal prior distribution truncated at 0 to guarantee the positivity of  $\theta_2$ . Simple linear regression, with maximum likelihood estimation, on available data at dose escalation will be used to estimate the model parameters  $(\theta_1, \theta_2, \nu)$ , thus providing the initial values for model parameter estimation by Bayesian approach; however, if insufficient data are available for estimation, (1, -1, 0.2) will be used as the initial values for  $(\theta_1, \theta_2, \nu)$ . Furthermore, the scale and shape parameters of the precision prior Gamma function are chosen to attain  $E(\nu)=0.2$  and  $\text{Var}(\nu)=0.04$ . Two chains will be run for the estimation of each parameter.

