Summary of Model Parameters for Part 1 - Posterior Distributions

PK Parameter on log scale Model Parameter	Mean	SD	MC error	5 th Percentile	Median	95 th Percentile
AUC[0-t] (µg.h/mL)						
Intercept	xxxx.x	xxxx.x	xxxx.x	xxxx.x	xxxx.x	xxxx.x
Slope of log dose	xxxx.x	xxxx.x	xxxx.x	xxxx.x	xxxx.x	xxxx.x
Precision	xxxx.x	xxxx.x	xxxx.x	xxxx.x	xxxx.x	xxxx.x
Cmax (µg/mL)						
Intercept	xxxx.x	xxxx.x	xxxx.x	xxxx.x	xxxx.x	xxxx.x
Slope of log dose	xxxx.x	xxxx.x	xxxx.x	xxxx.x	xxxx.x	xxxx.x
Precision	xxxx.x	xxxx.x	xxxx.x	xxxx.x	xxxx.x	xxxx.x

Note: The posterior distributions are derived from linear model  $\log\text{-PK-parameter} = \text{intercept} + \text{slope} \cdot \log\text{-dose} + \text{error term}$ .

Programmer note: Decimals will be adjusted to include approximately 5 significant digits.

GlaxoSmithKline

Example : PK\_T2  
Protocol : 204847  
Population : PK Parameter

Page 1 of n

Table 3.15  
Summary of Model Parameters for Part 2 - Posterior Distributions

PK Parameter on log scale Model Parameter	Mean	SD	MC error	5 th Percentile	Median	95 th Percentile
AUC[0-8]x3 (µg.h/mL)						
Intercept	xxxx.x	xxxx.x	xxxx.x	xxxx.x	xxxx.x	xxxx.x
Slope of log dose	xxxx.x	xxxx.x	xxxx.x	xxxx.x	xxxx.x	xxxx.x
Precision	xxxx.x	xxxx.x	xxxx.x	xxxx.x	xxxx.x	xxxx.x
Cmax (µg/mL)						
Intercept	xxxx.x	xxxx.x	xxxx.x	xxxx.x	xxxx.x	xxxx.x
Slope of log dose	xxxx.x	xxxx.x	xxxx.x	xxxx.x	xxxx.x	xxxx.x
Precision	xxxx.x	xxxx.x	xxxx.x	xxxx.x	xxxx.x	xxxx.x

Note: The posterior distributions are derived from linear model  $\log\text{-PK-parameter} = \text{intercept} + \text{slope} \cdot \log\text{-dose} + \text{error term}$ .

Programmer note: Decimals will be adjusted to include approximately 5 significant digits.

GlaxoSmithKline

Example : PK\_T3  
Protocol : 204847  
Population : PK Parameter

Page 1 of n

Table 3.16  
Summary of PK Parameters for Part 1 - Bayesian Prediction of Individual Subjects

PK Parameter Statistics	250 mg	500 mg	1000 mg	2000 mg	4000 mg	6000 mg
AUC[0-t] (µg.h/mL)						
n	xxx	xxx	xxx	xxx	xxx	xxx
Observed Mean	xxxx.x	xxxx.x	xxxx.x	xxxx.x	xxxx.x	xxxx.x
Predictive Distribution						
Mean	xxxx.x	xxxx.x	xxxx.x	xxxx.x	xxxx.x	xxxx.x
5 th Percentile	xxxx.x	xxxx.x	xxxx.x	xxxx.x	xxxx.x	xxxx.x
Median	xxxx.x	xxxx.x	xxxx.x	xxxx.x	xxxx.x	xxxx.x
95 th Percentile	xxxx.x	xxxx.x	xxxx.x	xxxx.x	xxxx.x	xxxx.x
Cmax (µg/mL)						
Observed Mean	xxxx.x	xxxx.x	xxxx.x	xxxx.x	xxxx.x	xxxx.x
Predictive Distribution						

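### Tables 3.16 and 3.17 print the mean of an individual's predicted AUC and Cmax, which has no finite value under the SAP's log-scale model, so the row is not a valid summary

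*SAP*

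**What the plan says.** The Bayesian model in SAP 8.2.2 regresses the log PK parameter on log dose. The error "is a random error term, with mean zero and variance" sigma squared. A normal error is implied by the coding remark "For ease of parameterization for the normal distribution in computer programming, use" the precision, nu = 1/sigma squared. SAP Table 9 gives nu the prior "Gamma(1, iscale=5" (shape 1, rate 5) and gives the intercept and slope almost flat normal priors, with the slope truncated at zero. Two chains of 10,000 draws each are kept.

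On reporting, 8.2.2 states: "The mean, median, and 5 th and 95 th percentiles (90% CrI) for each model parameter and prediction will be tabulated". The shell for Table 3.16, "Summary of PK Parameters for Part 1 - Bayesian Prediction of Individual Subjects", and its Part 2 counterpart, Table 3.17, place a predictive mean under the observed mean, in µg.h/mL and µg/mL. Tables 3.14 and 3.15 are labelled as log scale; 3.16 and 3.17 are not. The display list marks all of them as dose-escalation deliverables, and 8.2.2 says: "All the outputs discussed above and listed below are used together with safety and tolerability data to aid the next dose selection".

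One safeguard against skewness exists. The points of the dose-response plot "will be generated using the median as a measure of central tendency" if the distributions are skewed. It covers the figure, not the tables.

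**The concern.** A log-normal mean depends on the variance through exp(sigma²/2). When the precision is uncertain with a Gamma distribution, values of nu close to zero have positive density, and there exp(1/(2 nu)) grows faster than the Gamma density shrinks. The average over the posterior is then infinite. A program still prints a number, because it averages finitely many draws, but that number does not estimate a defined quantity.

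The convergence criteria in 8.2.2 would not reveal this. They are framed for the intercept, slope and precision, whose posteriors behave well. A team comparing the printed mean with the observed mean at a dose already given could read model misfit, or higher exposure than the data show, into a table meant to help choose the next dose in a first-in-human study.

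**Working it through.** **Prior as stated.** For Gamma(shape a, rate b), E = a/b = 1/5 = 0.2 and Var = a/b² = 1/25 = 0.04. Both match the SAP.

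**Existence of the mean.** With effectively flat priors on intercept and slope, the posterior is nu ~ Gamma(A, B), with A = 1 + (n-2)/2 and B = 5 + SSE/2. Given nu, the predicted mean is proportional to exp(c/(2 nu)) with c ≥ 1. The integral of exp(1/(2 nu)) · nu^(A-1) · exp(-B nu) diverges at nu = 0 for every A and B. Cutting it off at a lower bound shows the behaviour:

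| n | nu > 0.05 | nu > 0.01 | nu > 0.001 |
|---|---|---|---|
| 12 | 1.75 | 1.7×10¹⁰ | about 10¹⁹⁸ |
| 18 | 1.39 | 7.8×10³ | about 10¹⁸⁹ |
| 36 | 1.17 | 1.17 | about 10¹⁵⁹ |

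More data push the problem further into the tail but never remove it.

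**What would be printed.** Inputs:
- Medians from protocol Tables 8 and 9 (AUC 512 at 2000 mg, 1545 at 6000 mg; AUC(0-24) 3078 at 4000 mg TID).
- Log-SD = ln(95th/5th)/(2 × 1.645) = ln(640/409)/3.29 = 0.136. This is derived, not stated.
- True mean = median × exp(0.136²/2), so 517 at 2000 mg.
- SSE = (n-2) × 0.136², with data idealised at the medians.
- 20,000 draws per run, 400 seeds.

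Printed mean divided by true mean at the next planned dose:

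| Data available | n | Next dose | Median over seeds | 5-95% of seeds | Maximum |
|---|---|---|---|---|---|
| 250, 500, 1000 mg × 4 | 12 | 2000 mg | 2.55 | 2.42-2.94 | 6.1 |
| 250 to 2000 mg × 4 | 16 | 4000 mg | 1.68 | 1.65-1.73 | 1.76 |
| 250, 500, 1000 mg × 6 | 18 | 2000 mg | 1.60 | 1.57-1.63 | 1.65 |
| 250 to 4000 mg × 6 | 30 | 6000 mg | 1.23 | 1.22-1.24 | 1.25 |
| 1000, 2000 mg TID × 5 | 10 | 4000 mg TID | 6.2 | 5.0-26.4 | 4.75×10⁶ |
| 1000, 2000 mg TID × 8 | 16 | 4000 mg TID | 1.91 | 1.87-1.98 | 2.18 |

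Cohorts of 4 (Part 1) and 5 (Part 2) are the escalation minima in SAP 2.3; 6 and 8 are the full active cohorts in protocol 4.3.

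**Where the size comes from.** The posterior mean of sigma² is B/(A-1). At n=12, A = 6 and B = 5 + 10 × 0.0185/2 = 5.09, giving 5.09/5 = 1.02 against a planning value of 0.136² = 0.0185. At n=30, A = 15 and B = 5 + 28 × 0.0185/2 = 5.26, giving 5.26/14 = 0.38. The prior rate of 5 dominates B in both. With Gamma(0.001, 0.001) instead, the mean is still infinite, but the printed value is only 1.00 to 1.04 times the truth (up to 1.08 if the log-SD is 0.30), with a seed spread of about 1% or less.

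**What the other rows show.** At n=12 and 2000 mg the predictive median is 536, close to the true mean of 517. The predictive 95th percentile is 4149, against 640 in protocol Table 8.

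**The case against.** The strongest reply is that the infinite moment and the overstatement are separate matters. This stands. A diffuse Gamma prior leaves the mean just as infinite and almost removes the excess, so the fold figures measure the Gamma(1, iscale=5) prior. A reader might infer that the value is overstated because the mean is infinite; the calculations do not support that.

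A reader might also infer that the printed value always changes from run to run. It does not. From n of about 16, the 5-95% seed range at the next dose lies within about 4% of its median. If earlier Part 1 cohorts are complete, three dose levels give 6 + 6 + 4 = 16 subjects rather than 12, and the range at 2000 mg is 915 to 965.

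A third tempting reading is that the row would falsely show the NOAEL AUC of 2875 being exceeded throughout. At the planned Part 1 steps it would not, even with 4 active subjects per cohort: about 1310 at 2000 mg, 1740 at 4000 mg (n=16) and 2200 at 6000 mg (n=20). A 6000 mg column would print about 8,800 after the 1000 mg cohort, but protocol 4.2 limits the next step to 3-fold by then. At 4000 mg TID the planning median, 3078, already exceeds 2875. A false excess at a dose already given arises only at the Part 2 minimum: about 4010 at 2000 mg TID with n=10, against a true mean of about 1550.

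It is also fair that the median and percentiles sit in the same block and expose the skewness, that SAP 3.1 and protocol 9.3.2 single out threshold probabilities as the Bayesian aid to escalation, and that any distortion is upward. A back-transformed log-scale mean would be finite, but the SAP does not specify one, and the units and missing log-scale label point the other way. None of this gives the tabulated row a defined value.

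**Conclusion.** The point holds in limited form. The individual predictive mean in Tables 3.16 and 3.17 does not exist under the stated model, whatever the sample size, so the row should not be reported. Under the stated prior the printed value would exceed the true mean by about 1.2-fold (n=30), 1.6-fold (n=18) and 2.5-fold (n=12) at the next planned Part 1 dose, and by about 2-fold (n=16) to 6-fold (n=10) at 4000 mg TID. Instability between runs is material only at n of about 10 to 12.

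These figures rest on normal log-scale errors, averaging on the measurement scale, a log-SD of about 0.14 from protocol Table 8, and idealised data. The Part 2 figures also assume that the model is fitted to Part 2 data alone after two dose levels. The non-existence of the mean needs only the first two assumptions and the Gamma prior. The row informs escalation and does not decide it, so this is a correction worth making, not a flaw that undermines the design.

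**What to change.** In SAP 8.2.2 and the shells for Tables 3.16 and 3.17, remove the predictive mean and use the predictive median as the central value, keeping the 5th and 95th percentiles. Replace the observed mean with the observed geometric mean, so that like is compared with like. In the runs the median stayed within 0.97 to 1.05 of the true mean in Part 1 and 0.91 to 1.24 in Part 2, so it is much closer, though not exact at n=10.

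The cost is a sentence of SAP text and two shells with their program. Nothing well defined is lost.

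The SAP should not treat this as curing the Bayesian outputs. The 95th percentiles and the individual threshold probabilities remain inflated by the precision prior: at n=12 and 2000 mg, the probability of exceeding 3460 comes out near 6.5%, when the planning values imply essentially zero. That needs a separate revision of the Gamma prior in SAP Table 9.

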**Sensitivity and Supportive Statistical Analyses**

Not applicable.

### **8.2.3. Deviations from RAP Planned Analysis**

To ensure transparency, any deviations from the above analyses will be documented in a log appended to the CSR. These deviations may include (although are not limited to) algebraically different model parameterizations or changes in the prior structure to support convergence of the parameter estimations in SAS. These possible issues and solutions for them are discussed above in the appropriate sections.

## 10. APPENDICES

Section	Appendix
RAP Section 5 : General Considerations for Data Analyses & Data Handling Conventions	
Section 10.1	Appendix 1: Time and Events
Section 10.2	Appendix 2: Treatment States & Phases
Section 10.3	Appendix 3: Data Display Standards & Handling Conventions 
 
• Study Treatment & Sub-group Display Descriptors
 
• Baseline Definitions & Derivations
 
• Reporting Process & Standards
 

Section 10.4	Appendix 4: Derived and Transformed Data 
 
• General, Study Population & Safety
 
• Efficacy
 
• Pharmacokinetic
 
• Pharmacodynamic and or Biomarkers
 

Section 10.5	Appendix 5: Premature Withdrawals & Handling of Missing Data 
 
• Premature Withdrawals
 
• Handling of Missing Data
 

Section 10.6	Appendix 6: Values of Potential Clinical Importance
Section 10.8	Appendix 7: DMID Adult Toxicity Tables for Adverse Event Assessment
Section 10.8	Appendix 8: Multiple Comparisons and Multiplicity
Section 10.9	Appendix 9: Model Checking and Diagnostics for Statistical Analyses
Other RAP Appendices	
Section 10.10	Appendix 10: Abbreviations & Trade Marks
Section 10.11	Appendix 11: List of Data Displays

## 10.1. Appendix 1: Time & Events

### 10.1.1. Protocol Defined Time & Events

#### Time and Events Table: Screening and Day –1; Single and Repeat Dose Escalation (Part 1 and Part 2) and Single Dose (Part 3)

Procedure	Screening (up to 30 days before Day 1)	Day –1	Notes
Informed consent	X		
Inclusion and exclusion criteria	X	X	
Demography	X		
Medical history (includes substance usage and family history of premature cardiovascular disease)	X	X	Substances: drugs, alcohol, tobacco and caffeine.
Past and current medical conditions including cardiovascular medical history	X	X	
Safety and Laboratory Assessments			
SAE review	X	X	Serious AEs will be collected from the signing of informed consent.
Concomitant medication review	X	X	
Full physical examination including height and weight	X		
Brief physical examination		X	
Vital signs (BP, HR, oral temperature, respiration rate)	X	X	
12-lead electrocardiogram	X	X	
Continuous cardiac monitoring		X	Continuous dual-lead telemetry will be initiated on Day –1 at least 8 hours before study drug administration on Day 1.
Urine cotinine and drug and breath alcohol screens	X	X	
β-hCG pregnancy test/estradiol/FSH	X	X	Pregnancy test (if female of child-bearing age; serum at screening and urine at Day –1); estradiol and FSH at screening as appropriate. Only women of non-child-bearing potential may participate.
Human immunodeficiency virus antibody, hepatitis B surface antigen, and hepatitis C antibody screen	X		
Table is continued on the next page.			

Procedure	Screening (up to 30 days before Day 1)	Day -1	Notes
Clinical chemistry (including liver chemistries), hematology, and urinalysis	X	X	The albumin to creatinine ratio will be determined at Screening using the first morning void urine as described in protocol Section 7.3.7. An aliquot of the urine sample will be collected for NGAL and KIM-1 at Day -1. These samples may be analyzed after the end of the study if a clinical signal is detected. Instructions for collection and storage of these urine samples are included in the Study Reference Manual. Hematology assessments on Day -1 will also include total iron, total binding iron capacity, ferritin, and reticulocytes.
Genetic sample		X	Collect a pharmacogenomics sample only if the subject has a signed consent specific for this purpose. The pharmacogenomics sample can be collected anytime, but Day -1 is recommended. Informed consent for optional sub-studies (e.g., genetics research) must be obtained before collecting a sample.
Admission to clinical unit		X	

<math>\beta</math>-hCG = beta human chorionic gonadotropin, BP = blood pressure, FSH = follicle-stimulating hormone, HR = heart rate, KIM-1 = kidney injury molecule 1, NGAL = neutrophil gelatinase-associated lipocalin, SAE = serious adverse event.
			

**Time and Events Table: Part 1 - Single Dose Escalation and Part 3 – Single Dose**

Procedure	Day 1																Day 2	Day 3		
	Hours relative to treatment administration																			
	Pre-dose	0	0.5	1	1.25	1.5	2	3	3.5	4	4.5	5	6	8	10	12	16	24	36	48
Randomization	X																			
12-lead ECG 	X		X	X		X	X	X		X			X			X		X		X
Vital signs (BP, HR, oral temperature, respiration rate)	X		X	X		X	X	X		X			X			X		X		X
Fasting clinical chemistry, hematology, and urinalysis 																		X		
Treatment administration 		X																		
Blood collection for pharmacokinetics 	X		X	X	X	X	X	X	X	X	X	X	X	X	X	X	X	X	X	X
Urine collection for pharmacokinetics 	X	X								X				X		X		X		X
Continuous cardiac monitoring 	X	-----Continuous review----->																		
AE review		X	-----Continuous review----->																	
SAE review	X	-----Continuous review----->																		
Concomitant medication review	X	-----Continuous review----->																		
Discharge from inpatient unit 																				X

AE = adverse event, BP = blood pressure, ECG = electrocardiogram, HR = heart rate, SAE = serious adverse event.

NOTES:

1. Triplicate 12-lead ECGs to be obtained at least 5 minutes apart within 1 hour before dosing. Single ECGs will be obtained at all other time points.
2. An aliquot of the urine sample will be collected for neutrophil gelatinase-associated lipocalin (NGAL) and kidney injury molecule 1 (KIM-1). These samples may be analyzed after the end of the study if a clinical signal is detected. Instructions for collection and storage of these urine samples are included in the Study Reference Manual. The albumin to creatinine ratio will be determined using the first morning void urine on Day 2.
3. GSK3342830 or placebo will be administered as a single IV infusion in the morning on Day 1. The planned infusion duration time is 1 hour.
4. Pharmacokinetic blood samples will be collected for GSK3342830 and potential metabolites. At the end of the study the saved blood samples from a predicted therapeutically-relevant dose level and higher dose level for plasma PK analysis of parent and the highest dose level completed for metabolite profile, will be transferred to a GSK specified laboratory. Details of PK sample collection and storage will be provided in the Study Reference Manual.
5. Pooled urine samples will be collected over the following time intervals: pre-dose (within a 24-hour period before dosing, may begin on Day -1) and 0 to 4, 4 to 8, 8 to 12, 12 to 24, and 24 to 48 hours post-dose. Two aliquots of urine samples for baseline analysis may be collected from any time after admission to just before dosing on Day 1. At the end of the study, the saved urine samples from a predicted therapeutically-relevant dose level and higher dose level for urinary PK analysis of parent and the highest dose level completed for potential metabolite profile, will be transferred to a GSK specified laboratory. Urine will be collected in opaque bottles to maintain blind of blinded study site personnel. Details of urine sample collection and storage will be provided in the Study Reference Manual.
6. Continuous dual-lead telemetry will be initiated on Day -1 at least 8 hours before treatment administration on Day 1 and will continue until 48 hours post dose.
7. Subjects will be discharged from the clinical unit after the 48-hour post-dose assessments are complete.

**Time and Events Table: Part 2 - Repeat Dose Escalation**

Procedure	Study Day															
	1	2	3	4	5	6	7	8	9	10	11	12	13	14	15	16
Randomization	X															
12-lead ECG 	X	X	X	X	X	X	X	X	X	X	X	X	X	X	X	X
Vital signs (BP, HR, oral temperature, respiration rate) 	X	X	X	X	X	X	X	X	X	X	X	X	X	X	X	X
Fasting clinical chemistry, hematology, and urinalysis tests 		X			X					X					X	
Treatment administration 	X	X	X	X	X	X	X	X	X	X	X	X	X	X	X	X
Blood collection for pharmacokinetics 	X		X			X			X			X	X		X	
Urine collection for pharmacokinetics 	X	X													X	X
Continuous cardiac monitoring 	X←Continuous review→															
AE review	X←-----Continuous review----->															
SAE review	X←-----Continuous review----->															
Concomitant medication review	X←-----Continuous review----->															
Discharge from inpatient unit 																X

AE = adverse event, BP = blood pressure, ECG = electrocardiogram, HR = heart rate, SAE = serious adverse event.

NOTES:

1. Triplicate 12-lead ECGs will be obtained at least 5 minutes apart within 1 hour before the start of infusion (pre-dose) on Day 1. Single ECGs will be obtained at 0.5, 1, 1.5, 2, 3, 4, 6, and 12 hours after the start of infusion on Day 1 and Day 15, within 1 hour before the start of the morning infusion on Days 2, 3, 4, 5, 6, 7, 8, 9, 10, 11, 12, 13, and 14, and in the morning on Day 16.
2. Vital signs will be measured within 1 hour before the start of infusion (pre-dose) and at 0.5, 1, 1.5, 2, 3, 4, 6, and 12 hours after the start of infusion on Days 1 and 15, within 1 hour before the start of the morning infusion and on Days 2, 3, 4, 5, 6, 7, 8, 9, 10, 11, 12, 13, and 14, and in the morning on Day 16.
3. An aliquot of the urine sample will be collected for neutrophil gelatinase-associated lipocalin (NGAL) and kidney injury molecule 1 (KIM-1). These samples may be analyzed after the end of the study if a clinical signal is detected. Instructions for collection and storage of these urine samples are included in the Study Reference Manual. Hematology assessments on Days 5 and 15 will also include total iron, total iron binding capacity, ferritin, and reticulocytes. The albumin to creatinine ratio will be determined using the first morning void urine on Days 5 and 15.
4. GSK3342830 or placebo will be administered as a single IV infusion in the morning on Day 1, TID IV infusions (approximately every 8 hours) on Days 2, 3, 4, 5, 6, 7, 8, 9, 10, 11, 12, 13, and 14, and as a single IV infusion in the morning on Day 15. The planned infusion duration time is 1 hour.

Footnotes are continued on the next page.

5. Pharmacokinetic samples for GSK3342830 and potential metabolites will be collected on Day 1 at the following time points: pre-dose (within 15 minutes before dosing) and 0.5, 1 (end of infusion), 1.25, 1.5, 2, 2.5, 3, 3.5, 4, 4.5, 5, 6, 8, 10, 12, 16, and 24 hours after the start of infusion. Single pre-dose trough samples will be taken on the mornings of Days 3, 6, 9, 12, and 13. Serial samples will be collected on Day 15 at the following time points: pre-dose (within 15 minutes before dosing) and 0.5, 1 (end of infusion), 1.25, 1.5, 2, 2.5, 3, 3.5, 4, 4.5, 5, 6, and 8 hours after the start of infusion. At the end of the study, the saved blood samples from a predicted therapeutically-relevant dose level and higher dose level for plasma PK analysis of parent and from the highest dose level completed for potential metabolite profile will be transferred to a GSK specified laboratory. Details of PK sample collection and storage will be provided in the Study Reference Manual.
6. Pooled urine samples will be collected on Day 1 and Day 15 over the following time intervals: pre-dose (within a 24-hour period before dosing, may begin on Day -1) and 0 to 8 and 8 to 24 hours post-dose. Two aliquots of urine samples for baseline analysis may be collected from any time after admission to just before dosing on Day 1. At the end of the study, the saved urine samples from a predicted therapeutically-relevant dose level and higher dose level for urinary PK analysis of parent and from the highest dose-level completed for potential metabolite profile, will be transferred to a GSK specified laboratory. Urine will be collected in opaque bottles to maintain blind of blinded study site personnel. Details of urine sample collection and storage will be provided in the Study Reference Manual.
7. Continuous dual-lead telemetry will be initiated on Day -1 at least 8 hours before treatment administration on Day 1 and will continue until 48 hours post dose.
8. Subjects will be discharged from the clinical unit after the Day 16 assessments are complete.

